## 8. Research question and objectives

## 8.1 Research question

What is the safety profile and clinical effectiveness of rapidly infused CT-P10 in patients with NHL or CLL in the real world clinical setting?

## 8.2 Hypothesis

This is a descriptive study and there is no a priori hypothesis to be tested.

# 8.3 Primary research objective

To describe the incidence of IRR associated with rapid infusion of CT-P10 in patients with NHL or CLL on day 1 or day 2 after the index event (index event defined as the first rapid infusion of CT-P10, which must have been given as part of the second or a subsequent treatment cycle).

# 8.4 Secondary research objectives

To describe the following in patients who receive rapid infusion of CT-P10 for the treatment of NHL or CLL:

1. Safety profile in the 6 months post-index date (index date defined as the date of the first rapid infusion of CT-P10, which must have been given as part PASS PT Celltrion RAPID v2 0 FINAL 18APR2018

Page 19 of 43

of the second or a subsequent treatment cycle), including incidence (and frequency per patient per month, where appropriate) of the following safety events: IRRs, grade 3 or grade 4 IRRs, any adverse event (AE), any serious adverse event (SAE), any grade 3 or grade 4 AE, AEs as the primary cause for treatment discontinuation.

- 2. Clinical effectiveness in the 6 months post-index date (to be analysed separately for NHL and CLL), including overall survival (OS), progression free survival (PFS), best response, overall (complete/partial) response rate, time to complete or partial response.
- 3. NHL / CLL treatment patterns during the observation period (from diagnosis of NHL or CLL to 6 months post-index date), including types and doses of treatment, number and duration of infusions, time on treatment and reasons for discontinuation.
- 4. Patients' demographic, clinical, and NHL/CLL disease characteristics.

#### 9. Research methods

This study has been designed and will be conducted according to the requirements of the European Network of Centres for Pharmacoepidemiology and Pharmacovigilance (ENCePP; http://www.encepp.eu/index.shtml) and International Society for Pharmacoepidemiology (ISPE; https://www.pharmacoepi.org/resources/guidelines-08027.cfm) guidance, as appropriate.

# 9.1 Study design

[figure not shown]
This is a European, multi-centre, retrospective non-interventional postauthorisation safety study (PASS) based on secondary use of hospital medical records.

The study will involve the collection of patient-level data from hospital medical records (including infusion records) for patients with NHL or CLL who received treatment with CT-P10 in selected centres in five European countries. Patients will be selected based on the treatment they received as part of their standard clinical care in the real world.

Data will be collected retrospectively from the date of diagnosis of NHL or CLL until the index date (to capture patient's demographic and clinical characteristics), and for 6 months post-index (or until death, if sooner), to capture safety and clinical outcomes, as shown in 오류! 참조 원본을 찾을 수 없습니다. In cases where the full 6 month post-index observation period is not available at the time of initial patient identification/recruitment, the retrospective data collection will be undertaken in batches at agreed intervals throughout the observation period and completed once the full 6 months has elapsed.

A retrospective design was selected as most appropriate for collecting data since it is expected (based on scoping interviews with clinicians in the participating countries) that the outcomes of interest will be well-documented in patients' medical records, including the primary outcome (incidence of IRR), which will be recorded in infusion records. Furthermore, it will enable the results of the study to be available in a timelier manner than would be possible with a prospective design.

Figure 1: Study design

## 9.2 Setting

#### 9.2.1 Study population

The source population for this study is adult patients with NHL or CLL who received treatment with rapidly infused CT-P10 as part of their standard clinical care in five European countries.

Patients fulfilling the following criteria will be potentially eligible for inclusion in the study:

- Patients with a confirmed diagnosis of NHL (follicular lymphoma [FL] or diffuse large B-cell lymphoma [DLBCL]) or CLL.
- Patients who had received rapidly infused CT-P10 for their second or a subsequent treatment cycle; 'rapidly' defined as 90-minutes or less.
- Patients at least 18 years of age at the date of diagnosis of NHL or CLL.
- Patients (or next of kin, if appropriate locally) providing written informed consent for study data collection (if this is required according to local country regulations).

Patients fulfilling any of the following criteria will be excluded from the study:

- Patients who had received reference rituximab for any previous treatment cycles
   (i.e. prior to the index event) within the same line of treatment.
- Patients whose medical records are unavailable for review.

As only limited exclusion criteria will be applied, and patients will be included from a range of centres in five European countries, it is expected that the study population will be representative of the overall source population.

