#### 9.2.2 Patient identification and recruitment

Potentially eligible patients will be identified by members of the direct care team at each centre from hospital pharmacy records or other local department databases and assessed against the remaining eligibility criteria. Patients who meet all of the inclusion criteria and none of the exclusion criteria will be included in the study. All eligible patients at the participating centres will be included. If an insufficient PASS PT\_Celltrion RAPID\_v2 0 FINAL\_18APR2018

number of patients are identified at initial recruitment, a second round of (retrospective) recruitment may be undertaken at a later date, when more patients meet the eligibility criteria. Patients may be recruited to the study before the full 6 month post-index observation period has elapsed.

Patients (or their next of kin, if appropriate locally) will be approached by the local care team and invited to provide consent for study data collection, if this is required according to local country regulations.

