# Endpoint to address the secondary objective

# Variables required to address the secondary objective

Secondary objective 1: To describe the safety profile of rapidly infused CT-P10 in patients with NHL or CLL in the 6 months post-index date

- Proportion of patients who experience the following safety events in the 6 months post-index date, and frequency of each per patient per month:
  - Any IRR.
  - Any grade 3 or grade 4 IRR (according to the Common Terminology Criteria for Adverse Events [CTCAE] version 4).
  - Any other AE (excluding IRR).
  - Any other grade 3 or grade 4 AE (excluding IRR).
  - o Any serious adverse event (SAE).
- Proportion of patients with AEs as the primary cause for treatment discontinuation.
- Summary distributions of event type by grade.
- Proportion of all rapid CT-P10 infusions during which IRRs were experienced.

For all AEs (temporally associated with CT-P10 treatment) during the 6 months post-index (including the index date):

- Description of AE
- IRR (Yes/No)
- Event start date
- Event end date
- Seriousness
- CTCAE v4.0 grade
- Clinician's assessment of relationship to CT-P10
- AE resulted in treatment discontinuation (Yes/No).

Secondary objective 2: To describe the clinical effectiveness of rapidly infused CT-P10 in patients with NHL or CLL in the 6 months post-index

- OS, defined as the time from the index date until death from any cause.
- Proportion of patients surviving at six months following NHL or CLL diagnosis and following the index date.
- PFS, defined as the time from the index date until the first documented evidence of disease progression or death from any cause.
- Proportion of patients surviving and free from disease progression at six months following the index date.
- Summary of best response to CT-P10

- Date of data collection.
- Patient alive at 6 months post-index (Yes / No / Not known)?
- If no, date of death (DD/MM/YYYY).
- All treatment response assessments in the post-index period (date, recorded treatment response [complete response / partial response / no response or stable disease / progressive disease], assessment based on IWCLL / Revised Response Criteria for Malignant Lymphoma / local criteria / other criteria, type(s) of

- (complete response / partial response / no response or stable disease / progressive disease).
- Proportion of patients achieving a complete or partial response.

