#### 9.9 Limitations of the research methods

- Patient or next of kin consent may be a requirement for this study in some of the participating countries; this may introduce selection bias, resulting in a study sample that may not be representative of the wider patient population of
- **Thterest**erpretation of data collected retrospectively will be dependent on the completeness and quality of the medical records and the reliability of the abstraction of data from the medical records.
- The primary endpoint of this study is the incidence of IRR on day 1 or day 2 after the index event. It is expected (based on scoping interviews) that IRRs occurring during or shortly after the CT-P10 infusion should be reliably documented in

patients' infusion records, however, it is possible that IRRs occurring the day after the infusion may be less well-documented. This may result in an underestimate of the overall incidence of IRR during the observation period, particularly of milder events. The IRR rate may also be underestimated as a result of the definition of a rapid infusion as 90 minutes or less, since this may result in the exclusion of cases where the initial intention was to infuse CT-P10 over 90 minutes, but the infusion was delayed or stopped due to IRRs.

- The patient records included in this study will be from physicians and study sites
  that are willing to participate. Therefore, study findings may not be generalisable
  to all patients with NHL or CLL treated with rapid infusion of CT-P10 or to all
  physicians who treat these patients in the participating countries.
- As this is a non-interventional study conducted in a routine clinical practice setting, the assessment of treatment response may not be uniform, particularly with regard to the timing of evaluations. In particular, it is likely that disease progression for the identified patients will have been monitored at less frequent intervals than would be required in a clinical trial and therefore progression events will be identified later. This may result in upwardly biased estimates of PFS. For this reason, any findings regarding the endpoints of clinical response should be considered to be 'real world estimates' which may not be directly comparable to those observed in clinical trials.
- This is a descriptive study and no adjustments to control for confounding will be carried out.

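### If any country requires consent and does not accept it from next of kin, patients who die before being approached are lost while survival is counted from the earlier index infusion, which flatters OS and fatal SAEs

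*Protocol*

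**What the plan says.** - **Eligibility (Protocol 9.2.1).** Exposure is already in the past at recruitment: "Patients who had received rapidly infused CT-P10 for their second or a subsequent treatment cycle; 'rapidly' defined as 90-minutes or less". Consent is a further criterion wherever local rules demand it: "Patients (or next of kin, if appropriate locally) providing written informed consent for study data collection".
- **Timing of consent (9.2.2).** Patients are found from pharmacy or departmental records. They or their next of kin "will be approached by the local care team and invited to provide consent for study data collection, if this is required" by local rules. Recruitment may take place before the 6 months are complete. It may also be late: if an insufficient "number of patients are identified at initial recruitment, a second round of (retrospective) recruitment may be undertaken at a later date".
- **Time origin (9.3, secondary objective 2).** "OS, defined as the time from the index date until death from any cause". PFS has the same origin and counts death as an event. Section 9.7.2 runs the Kaplan-Meier plots from the index event and does not provide for later entry to the risk set.
- **Fatal events (2.2, 9.3).** Death is one of the SAE criteria, and SAEs over the 6 months after index are a secondary endpoint.
- **What is conceded (9.9).** Consent may be needed in some countries, and "this may introduce selection bias, resulting in a study sample that may not be representative of the wider patient population". No direction is given, and no endpoint is named.
- **What is absent.** The variables in 9.3 include a date of data collection but no consent date or consent route. Centres are pooled (9.7), and 9.7.4 plans no sensitivity analyses.

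**The concern.** In a country that requires consent and does not take it from next of kin, a patient must be alive when approached in order to be included. The time from index infusion to approach is then time in which no included patient can have died, yet the analysis counts it as time at risk. The deaths that go missing are OS events, the death component of PFS, and fatal SAEs, so the error can only be favourable. In a post-authorisation safety study that is the awkward direction.

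If some countries are affected and others are not, the pooled OS depends partly on national consent rules. Eligibility, collected variables and time origin are all set in the protocol. Without a consent date and a count of patients lost, a later analysis plan could neither correct the effect nor show that it is absent.

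**Working it through.** **The protocol's own figure.** The only precision figure concerns the primary endpoint: 6.8% to 14.0% for a 10% IRR rate in 300 patients (9.5). An exact interval for 30/300 reproduces it. It is not an input here. The protocol states no survival rate, no approach time and no list of consent countries.

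**Could the gap be long?** Approval was in February 2017 (section 7) and data collection starts in May 2018 (section 6), so an index infusion could precede the start of collection by up to about 15 months. Approaches both before and after month 6 are therefore possible. The documents do not say which is usual.

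**Inputs**
- c, the share of the source cohort in affected countries: 0.2 for one country and 0.4 for two, from about 60 of 300 per country (9.2.4).
- S, the true 6-month OS: 90%, assumed.
- A, the time from index to approach: assumed either uniform over months 0 to 6, or exactly month 6.
- Survival is exponential from index. In affected countries a patient is included only if alive at A.

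**Formula.** For A no later than month 6, let P be the probability of being alive at approach. Then

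naive 6-month OS = S / [c·P + (1 − c)].

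**Approach uniform over 0 to 6 months.** P = (1 − 0.9)/(−ln 0.9) = 0.1/0.10536 = 0.9491.
- One country: 0.9/(0.2 × 0.9491 + 0.8) = 0.9/0.9898 = 90.9%. Deaths seen per 300 source patients: 300 × [0.2 × 0.0491 + 0.8 × 0.1] = 26.9 of 30.
- Two countries: 0.9/(0.4 × 0.9491 + 0.6) = 0.9/0.9796 = 91.9%. Deaths seen: 23.9 of 30.

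**Every approach at month 6.** P = 0.9.
- One country: 0.9/0.98 = 91.8%. Deaths seen: 24 of 30.
- Two countries: 0.9/0.96 = 93.8%. Deaths seen: 18 of 30.
- Within an affected country, naive OS is 100%.

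Later approaches change the pooled figure little. At month 12, P = 0.81, and one country gives (0.2 × 0.81 + 0.8 × 0.9)/(0.2 × 0.81 + 0.8) = 0.882/0.962 = 91.7%; two give 0.864/0.924 = 93.5%. Taking 60 per country as the number recruited rather than the source number, the month-6 results are (240 × 0.9 + 60)/300 = 92.0% and (180 × 0.9 + 120)/300 = 94.0%.

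**Other true rates** (uniform approach, then month 6)

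| True OS | One country | Two countries |
|---|---|---|
| 95% | 95.5%, 96.0% | 96.0%, 96.9% |
| 80% | 81.7%, 83.3% | 83.5%, 87.0% |

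**Does delayed entry repair it?** With S = 90%, uniform approach and all patients affected, a simulation of 2,000,000 patients gives a naive OS of 94.8%, matching 0.9/0.9491. Entering patients in the risk set at approach returns 90.0%, the true value. Where every approach falls at or after month 6, no time at risk remains in affected countries and delayed entry cannot help.

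**The case against.** **The trigger is not shown.** The mechanism needs a country that both requires consent and refuses next of kin. The protocol names none, limits consent to where regulations demand it, and offers next of kin as a route wherever locally appropriate. This stands. A reader might infer that OS is biased as a matter of fact; the documents support only the conditional statement. If next-of-kin consent is accepted and obtained, or consent is not required, the mechanism disappears.

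**The size can be overdrawn.** With 8% true mortality, three of five countries affected and every approach at month 6, pooled mortality reads 9.6/285.6 = 3.4%, less than half the truth. A reader might take this as the expected effect. Nothing in the documents supports three affected countries or uniformly late approach, and 9.2.2 expressly allows recruitment before month 6. The pooled figure is also not a planned result, because effectiveness is reported separately for NHL and CLL. Under the milder assumptions the shift is 1 to 2 points. The sampling half-width at 90% is 1.96 × √(0.09/240) = 3.8 points for 240 NHL patients and 1.96 × √(0.09/60) = 7.6 points for 60 CLL patients.

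**PFS is not hit as hard as OS.** Living patients who have progressed can still consent. PFS is distorted only through those who die before approach. This stands.

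**It is already conceded, and the rest is for the analysis plan.** Section 9.9 does admit selection bias from consent. However, for assessment timing the same section says that PFS is biased upward, while for consent it gives neither direction nor endpoint, and OS receives no warning. Delayed entry could be left to an analysis plan, but the data it needs must be collected under the protocol.

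**The consequence is limited.** The study is descriptive, OS and PFS are secondary, and IRR on day 1 or 2 is touched only through any link between a reaction and early death. This stands.

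**Conclusion.** The concern holds conditionally. Wherever consent is required and deceased patients cannot be included through next of kin, the rules as written lose deaths before approach while counting survival from index. OS is then too high and fatal SAEs too low, and PFS is too high through patients who die before approach. The direction is the same in every scenario examined.

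At a true 6-month OS of 90%, the overstatement is about 1 to 2 points with one country affected and 2 to 4 points with two. This assumes exponential survival, equal country shares, and approach either spread over months 0 to 6 or all at about month 6. The documents do not establish that any country is affected, that the loss is larger than this, or that the primary endpoint is compromised.

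**What to change.** 1. Record in the eDCF the consent date and the consent route (patient, next of kin, or not required).
2. Have each site log how many otherwise eligible patients were not included because they died before consent. This count alone shows whether the problem exists.
3. For affected sites, analyse OS and PFS, separately for NHL and CLL, with entry to the risk set at the consent date.
4. Where most approaches fall after month 6, present OS, PFS and fatal SAE proportions from the sites where deceased patients can be included, and show affected sites separately. The fatal SAE proportion needs this display in any case, because delayed entry does not apply directly to a simple proportion.
5. State in 9.9 that selection through consent biases OS and PFS upward and fatal SAEs downward.

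**Cost.** Two eDCF fields, one log count per site and a few sentences. Patients consented late contribute little or no time, so OS and PFS lose precision, and delayed entry discards PFS events that occurred before consent.

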#### 9.2.2 Patient identification and recruitment

Potentially eligible patients will be identified by members of the direct care team at each centre from hospital pharmacy records or other local department databases and assessed against the remaining eligibility criteria. Patients who meet all of the inclusion criteria and none of the exclusion criteria will be included in the study. All eligible patients at the participating centres will be included. If an insufficient PASS PT\_Celltrion RAPID\_v2 0 FINAL\_18APR2018

number of patients are identified at initial recruitment, a second round of (retrospective) recruitment may be undertaken at a later date, when more patients meet the eligibility criteria. Patients may be recruited to the study before the full 6 month post-index observation period has elapsed.

Patients (or their next of kin, if appropriate locally) will be approached by the local care team and invited to provide consent for study data collection, if this is required according to local country regulations.

#### 9.2.3 Observation period

Data will be collected retrospectively for each patient from the date of diagnosis of NHL or CLL until the index date and for a period of 6 months post-index (or until death, if sooner).

#### 9.2.4 Study sites

Study sites will be specialist treatment centres or hospitals which routinely use CT-P10 in the treatment of patients with NHL or CLL, recruited from five European countries (the UK, Spain, France, Italy and the Netherlands). Based on the target sample size, each country will recruit approximately 60 patients. To reduce any bias potentially arising from using a single site in one country, at least two centres in each country will be included to meet the country targets. Centres will be selected based on their current practice of rapidly infusing CT-P10.

#### 9.3 Variables

The exposure of interest in the present study is treatment with CT-P10, administered by rapid infusion as part of the second or a subsequent treatment cycle. All study patients will be exposed by definition, as this is specified in the inclusion criteria.

The endpoints associated with each of the study objectives are described below, along with the variables that will be collected in order to address the objectives. Response options for each variable will be further detailed in the electronic data collection form (eDCF).

The endpoints below will be reported using descriptive statistics of distribution, central tendency and dispersion, as appropriate for the data collected.

# Endpoint to address the primary objective

# Variables required to address the primary objective

Primary objective: To describe the incidence of IRR associated with rapid infusion of CT-P10 in patients with NHL or CLL on day 1 or day 2 after the index event (index event defined as the first rapid infusion of CT-P10, which must have been given as part of the second or a subsequent treatment cycle).

Proportion of patients who experience an IRR\* on day 1 or day 2 after the index event.

- Did IRR(s) occur on day 1 or day 2 after the index event (Yes/No)?
- \* An IRR is defined as any AE from a predefined list (see Annex 3) occurring on day 1 or day 2 after an infusion of CT-P10.
- If yes, IRR description and date

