## 2.2 Key definitions

- **Index event:** first rapid infusion of CT-P10 (note: first rapid infusion must have been given as part of the second or a subsequent treatment cycle).
- **Index date:** date of first rapid infusion of CT-P10 (note: first rapid infusion must have been given as part of the second or a subsequent treatment cycle) (day 1).
- **Rapid infusion:** defined as a total infusion time for CT-P10 of 90 minutes or less.
- **Infusion-related reaction (IRR):** any adverse event (AE) from a pre-defined list (see Annex 3) occurring on day 1 or day 2 after an infusion of CT-P10.
- Pre-index observation period: the pre-index observation period for this study
  will be from the date of diagnosis of NHL or CLL until the index date, and will be
  used to capture patients' demographic and clinical characteristics.
- Post-index observation period: patients will be observed for a period of 6
  months after the index date (or until death, if sooner), to capture safety and
  clinical outcomes.
- Adverse event (AE): An AE is any untoward medical occurrence in a patient administered a pharmaceutical product and which does not necessarily have to have a causal relationship with this treatment. An AE can therefore be any unfavourable and unintended sign (including an abnormal laboratory finding, for example), symptom, or disease temporally associated with the use of a medicinal product, whether or not considered related to the medicinal product. The definition of an AE includes worsening of a pre-existing medical condition.

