# Annex 3. Additional information: Infusion related reactions to be captured

The following adverse events are included in the definition of an infusion related reaction and will be captured in this study:

- Abdominal pain
- Anaphylactoid reaction
- Anaphylaxis
- Angina pectoris
- Angioneurotic oedema
- Asthenia
- Bronchospasm
- Cardiac arrhythmia
- Cardiac failure
- Chills/rigors
- Cyanosis
- Diarrhoea
- Dizziness
- Dyspnoea
- Erythema

- Fatigue
- Generalised oedema
- Headache
- Hot flush
- Hypersensitivity
- Hypertension
- Hypotension
- Laryngeal oedema
- Myocardial infarction
- Nausea
- Oropharyngeal pain
- Peripheral oedema
- Pruritus
- Pyrexia
- Rash
- Rhinitis
- Tachycardia
- Throat irritation
- Urticaria
- Vomiting
- Wheezing

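### The primary infusion-reaction rate has no causality condition, so it can include symptoms of co-administered chemotherapy, and the plan neither discloses this nor reports a related-event rate beside it

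*Protocol*

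**What the plan says.** The protocol's primary objective (section 8.3) is to describe IRRs associated with rapid infusion of CT-P10. Section 9.3 defines an IRR for this purpose as "any AE from a predefined list (see Annex 3) occurring on day 1 or day 2 after an infusion of CT-P10". Section 2.2 numbers the index date as day 1 ("Index date: date of first rapid infusion of CT-P10"), so the window is the infusion day and the next calendar day. The same section says that an adverse event "does not necessarily have to have a causal relationship with this treatment".

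Annex 3 supplies the list: "The following adverse events are included in the definition of an infusion related reaction and will be captured in this study". It has 36 terms. Some are fairly specific to a reaction (anaphylaxis, bronchospasm, urticaria). Others are not: nausea, vomiting, diarrhoea, fatigue, asthenia, headache, abdominal pain.

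The primary variable is "Did IRR(s) occur on day 1 or day 2 after the index event (Yes/No"), followed, if yes, by a description and a date. The survival item in the same section has a third option: "Patient alive at 6 months post-index (Yes / No / Not known").

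Under secondary objective 1, section 9.3 collects start date, end date, grade and the clinician's "assessment of relationship to CT-P10" for adverse events from the index date onward. Under secondary objective 3 it records any chemotherapy regimen given with CT-P10. Section 9.7.1 plans a Z-test of the observed IRR rate against published rates for reference rituximab. Section 9.7.4 plans no sensitivity analyses. Section 9.9 concedes that "it is possible that IRRs occurring the day after the infusion may be less well-documented" and names underestimation as the consequence.

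**The concern.** The objective asks about reactions associated with the infusion; the endpoint counts listed symptoms close in time to it. The two can differ in a population where some patients receive chemotherapy with the antibody, because several listed symptoms are ones that chemotherapy can also cause. Nothing in the primary definition removes such events, although the field that would identify them is collected.

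Two features of data capture add to this. With dates but no times, the dataset cannot show whether a symptom on the infusion day began before or after the infusion. With no visible option for an undocumented day 2, a chart that is silent about day 2 may be indistinguishable from one recording no event.

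Section 9.9 discusses bias in one direction only. A reader of it would take the reported rate as, if anything, a floor, whereas the definition also allows inflation. The rate is the study's headline result and is to be tested against the literature, so a shift caused by the definition could be read as a property of CT-P10.

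**Working it through.** **1. The plan's own precision figure.** For an IRR rate of 10% in 300 patients, section 9.5 gives a 95% confidence interval of 6.8% to 14.0%. The exact (Clopper-Pearson) interval for 30/300 is 6.8% to 14.0%, so the figure reproduces. It covers sampling error only, not misclassification in either direction.

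**2. Inflation from unrelated symptoms.** Let t be the rate of true infusion reactions and q the proportion of patients with a listed symptom on day 1 or 2 from another cause. If the two are independent, the recorded rate is 1 − (1 − t)(1 − q). Take t = 8.84%, the meta-analysis rate in section 9.5. The documents give no value for q, so 3%, 5% and 10% are assumptions.

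- q = 3%: 1 − 0.9116 × 0.97 = 11.6%
- q = 5%: 1 − 0.9116 × 0.95 = 13.4%
- q = 10%: 1 − 0.9116 × 0.90 = 18.0%

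**3. What that would do to the Z-test.** Assume a one-sample test against 8.84% treated as fixed, n = 300, two-sided 5%. Section 9.7.1 names neither the comparator value nor the level. The standard error is √(0.0884 × 0.9116 / 300) = 1.639 percentage points. The upper limit is 8.84 + 1.96 × 1.639 = 12.05%, or 36.2 patients, so rejection starts at 37/300 = 12.3%. The lower limit is 5.63%, or 16.9 patients, so 16 or fewer also rejects. Exact binomial probabilities of rejection when the true reaction rate equals the comparator are:

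| q (assumed) | Recorded rate | Probability of rejecting 8.84% |
|---|---|---|
| 0% | 8.8% | 4% |
| 3% | 11.6% | 37% |
| 5% | 13.4% | 73% |
| 10% | 18.0% | >99% |

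**4. Loss of day 2 events.** Let s be the share of reactions that occur on day 2 only and m the share of those that go unrecorded; neither is in the documents. If unrecorded events are counted as 'No', the recorded rate is true rate × (1 − s × m). For a true rate of 10%:

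- s = 10%, m = 20%: 9.8%
- s = 30%, m = 50%: 8.5%
- s = 50%, m = 80%: 6.0%

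**5. Both together.** With t = 8.84%, q = 5%, and the day 2 loss applied equally to all listed events, 13.4% becomes 13.1%, 11.4% or 8.0% under the three day 2 settings. The net direction relative to 8.84% therefore depends on inputs that nobody has.

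**6. Why the third response option matters.** Section 9.7.3 restricts each analysis to patients with data. If 30 events are recorded and 30 or 60 event-free patients have no day 2 documentation, counting them as 'No' gives 30/300 = 10.0%. Leaving them out gives 30/270 = 11.1% or 30/240 = 12.5%. The rule can be applied only if the form separates the two states.

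**The case against.** A fixed list with a fixed window is reproducible across sites in five countries and needs no judgement from the chart reviewer. A causality-filtered rate brings its own missing data. That is a good reason to keep the Annex 3 count as primary, but it does not argue against a second rate beside it.

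Much of the remedy can be tabulated from planned data, and the statistical analysis plan may already contain such tables. That is fair for the related-event rate and for splitting recorded events by day. It does not cover onset relative to the infusion or day 2 documentation status, which no analysis plan can recover if they are not abstracted. Nor does it cover the one-sided discussion in section 9.9.

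A reader might infer that the protocol codes an undocumented day 2 as 'No' and so defeats its missing-data rule. The documents do not say so. Section 9.3 leaves the detail of response options to the data collection form, which is not shown, and section 9.7.3 calls for available cases. Weak day 2 recording is also openly disclosed.

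A reader might also infer that a symptom already present before the infusion counts. The definition says after an infusion, so it is not meant to. The narrower point, that same-day sequence cannot be checked from dates, stands.

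Finally, one might hold that the rate cannot be compared with the literature because published rates use attributed events. The documents do not say how the cited studies defined an IRR. If they counted any listed symptom, a filtered day 1 rate would be the worse match.

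**Conclusion.** The point holds in a limited form. The primary rate has no causality condition, its list contains non-specific symptoms that chemotherapy given with CT-P10 can produce, and the protocol acknowledges only downward bias. The available dates cannot establish same-day sequence, and missing day 2 information may not be separable from 'No'.

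The size is unknown. The shift from 8.84% to between 11.6% and 18.0% rests on assumed unrelated-symptom rates of 3% to 10%, on independence, and on treating 8.84% as a rate free of such symptoms. The test results further assume that 8.84% is the fixed comparator. Loss of day 2 events works the other way, so the net direction cannot be stated. The stated sample-size precision at 10% is correct and unaffected. This is an inexpensive improvement that brings the primary result closer to its objective; it does not show that the endpoint is invalid.

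**What to change.** Keep the Annex 3 rate as the primary endpoint. Pre-specify beside it:

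- the proportion of patients with a day 1-2 IRR that the clinician judged related to CT-P10, from the field already collected, with the number lacking a causality assessment;
- the rate for day 1 alone and for day 1-2, with the number of patients whose day 2 is undocumented.

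In the data collection form, add a 'Not documented' option for day 2 and an item for onset before or after infusion start. These must be in place before abstraction begins. In section 9.9, add that symptoms from causes other than the infusion, including co-administered chemotherapy, may raise the rate. For any comparison with the literature, use the version whose definition matches the cited source and state that definition; do not prescribe the attributed day 1 rate in advance.

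The cost is a few form options, a few table rows and slightly more abstraction work. Causality will be missing for some records, so the related-event rate should be read with that count beside it.
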